5.3 Daily Diary

The subjects will record daily in the Patient Chest Tube Diary or using the Medidata Patient Cloud App. Attachment 14.1.

5.4 Twice Weekly Telephone Calls (Group 1 Only)

The subjects in Group 1 will receive twice a week telephone calls from their coordinating medical team. Attachment 14.2.

5.5 Off Study

Subjects will be followed for 30 days following discharge from the hospital or until the chest tube has been removed if it remains in place for more than 30 days post hospital discharge. The patient will be instructed to return their Patient Chest Tube Diary at their next visit or via mail if they did not use the electronic app. A telephone call may be made in order to remind the participants to return their daily diary. Attachment 14.3.

Schedule of Events						
Study Activity	Visit 1	Visit 2	Daily Diary	Twice Weekly Calls ^a	Off Study	
Informed Consent	х					
Air Leak Status	Х					
Surgical History	Х					
Patient Education		х				
Patient Chest Tube Diary			x			
Telephone Assessment				Х		
Adverse Event Evaluation			Х	Х	х	
a: Group 1 only. b: Includes microbiology assessment of infection if done as part of clinical care and data is available.						

6 Statistical Plan

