3.1 General Description

This study is a multicenter, randomized trial for the treatment of subjects discharging from the hospital with a chest tube and valve in place. Subjects will be screened prior to discharging from the hospital and interested qualified subjects will be consented and offered participation in this trial. Once consent has been obtained the subject will be randomized to receive oral antibiotics and close monitoring, defined as twice weekly telephone calls by a member of the care team, of their chest tube and valve or standard of care, defined as no calls from the care team but waiting for the subject to contact the care team when the air leak has stopped. The subject will be followed until they have their chest tube removed.

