3.6 Identification of Source Data

The following source data will be directly recorded on the Case Report Form (CRF):

• Patient Chest Tube Diary

The following source data will not be directly collected in the Case Report Form (CRF), but will be captured in supportive documentation (study source documents, electronic medical record):

- Laboratory results and clinical interpretation of the values
- Clinical significance of observations
- Hospital admissions

4 Subject Selection Enrollment and Withdrawal

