6.1 Sample Size Determination

A power analysis was done to determine the sample size. The differences in rates of empyema and 30-day readmission we explored using a two-sided test at an alpha-level of 0.05 and for 80% power. Rate reductions of 25%, 50% and 75% were evaluated. A reduction rate of 50% was selected for empyema and will require 253 patients in each arm for a total enrollment of 506 patients. In allowing an additional 10% for drop outs a total target enrollment of 560 patients will be needed. The 560 patients will give a rate reduction between 25% and 50% for 30-day readmission.

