7.2 Recording of Adverse Events

At each contact with the subject, the study team must seek information on adverse events by specific questioning and, as appropriate, by examination. Information on all adverse events should be recorded immediately in the source document, and also in the appropriate adverse event section of the case report form (CRF). All clearly related signs, symptoms, and abnormal diagnostic, laboratory or procedure results should recorded in the source document.

Adverse event data related to the indwelling chest tube, valve, ongoing air leak, or antibiotic use (group one) occurring during the study period must be recorded. The clinical course of each event should be followed until resolution, stabilization, or until it has been ultimately determined that the study treatment or participation is not the probable cause. Serious adverse events that are still ongoing at the end of the study period must be followed up, to determine the final outcome. Any serious adverse event that occurs during the Adverse Event Reporting Period and is considered to be at least possibly related to the study treatment or study participation should be recorded and reported immediately.

CTCAE Version 5.0 (v5.0: November 27, 2017) will be used to standardize classification and grading of Adverse Events.

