14.3 Diary Return Telephone Script

Diary Return Telephone Script

Protocol Title: A Randomized Study Evaluating Patients Discharged with Indwelling Chest Tube and Valve IRB #: 17-007774

Principal Investigator: [name]

Introduction:

Hello, this is _____ calling from the Mayo Clinic in Rochester, Minnesota (if out of state). May I please speak to _____?

***1f the participant is there continue with the script.

***If the participant is not there, ask when it would be a good time to speak with ?

Describe the Reason for the Call:

As you may recall you agreed to participate in A Randomized Study Evaluating Patients Discharged with Indwelling Chest Tube and Valve and you were asked to complete a daily diary about your indwelling chest tube. We are calling to confirm that if your chest tube has been removed that you have returned your Patient Chest Tube Diary.

Has your chest tube been removed?

🗆 No

If no, as a reminder when it has been removed please note that on your diary and send it back in the provided envelope. If you do not have your envelope we would be happy to send one out to you.

Yes

If yes, have you returned your diary?

🗆 No

If no, as a reminder please send it back in the provided envelope. If you do not have your envelope we would be happy to send one out to you.

□ Yes

If yes, thank you so much for returning the diary.

Closing

Thank you for participating in our research study. Please understand that your answers will remain confidential. Give them some follow-up contact information (name and telephone number) in case they think of any more questions afterwards.

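### Group 1 has scheduled calls at which 30-day empyema and readmission can surface; Group 2 has no equivalent mandatory contact, so events treated elsewhere may be recorded unequally

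*Protocol*

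**What the plan says.** **Scheduled contact.** Protocol 5.4 states: "The subjects in Group 1 will receive twice a week telephone calls from their coordinating medical team". Protocol 3.1 describes the comparator as "standard of care, defined as no calls from the care team but waiting for the subject to contact the care team" once the leak has stopped.

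**Adverse-event questioning.** Protocol 7.2 states: "At each contact with the subject, the study team must seek information on adverse events by specific questioning". The Schedule of Events in 5.5 marks adverse-event evaluation at the daily diary, at the twice-weekly calls (Group 1 only) and at Off Study.

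**Study end.** Protocol 5.5 provides one call that could reach both groups, and it is optional: "A telephone call may be made in order to remind the participants to return their daily diary". Its script (14.3) gives the purpose as: "We are calling to confirm that if your chest tube has been removed that you have returned your Patient Chest Tube Diary". It asks about tube removal and diary return and nothing else.

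**Content of the attached forms.** The diary (14.1) asks about air leak, and in Group 1 about antibiotic intake, with space for comments. The twice-weekly script (14.2) asks about air leak, any change in it, and one open question about the tube and valve.

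**Records.** Protocol 3.6 says that laboratory results and hospital admissions "will be captured in supportive documentation (study source documents, electronic medical record"), without distinction by arm. It does not mention admissions to hospitals whose records the site does not hold.

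**The concern.** Both endpoints are events within 30 days of discharge, and the primary objective in section 2 counts empyema only when it is documented. An event that never reaches the site's records is therefore analysed as no event. If one arm has regular conversations in which such an event can come up and the other does not, the recorded rates can differ even when the true rates do not.

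Two effects of the calls must be kept apart. If a call leads to earlier action and so prevents an empyema or an admission, that is part of the randomised strategy and belongs in the treatment effect. If a call only causes an event to be written down that would have gone unrecorded in Group 2, that is bias.

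The second effect works against Group 1: it can mask a real benefit or suggest harm. The intention-to-treat analysis in 6.2 does not repair it. Nor do the Kaplan-Meier and Cox analyses, which deal with follow-up known to be incomplete and not with events never recorded.

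**Working it through.** **Inputs**
- Protocol 6.1: "using a two-sided test at an alpha-level of 0.05 and for 80% power"; "A reduction rate of 50% was selected for empyema and will require 253 patients in each arm".
- Control empyema rate: 6.1 states none. I assume 16.5%, from the referral-center study described in 1.2, which gives 8.25% after a 50% reduction.
- Share of Group 2 events captured, s: not in the documents. It is varied below, with capture in Group 1 set to 100%.

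**Step 1. The plan's own figure.** Let p1 = 0.165, p2 = 0.0825 and p̄ = (p1 + p2)/2 = 0.12375. Then

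n = [1.960·√(2p̄(1−p̄)) + 0.842·√(p1(1−p1) + p2(1−p2))]² / (p1−p2)² = 249 per arm.

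This is within 2% of the stated 253, so 16.5% is a plausible reading of the planning rate. The sample size itself is not in question.

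**Step 2. Number of calls.** Two per week over 30 days gives 2 × 30/7 = 8.6, so about 8 to 9 calls. This is a maximum: the protocol does not say that calls continue after tube removal. The matching number of scheduled calls in Group 2 is zero.

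**Step 3. True halving, Group 2 under-captured.** The observed control rate is a = 0.165·s and the observed Group 1 rate is b = 0.0825. With 253 per arm, d = |a−b| and p̄ = (a+b)/2:

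SE0 = √(2p̄(1−p̄)/253), SE1 = √([a(1−a) + b(1−b)]/253), power = Φ((d − 1.960·SE0)/SE1).

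For s = 0.90: a = 0.1485, d = 0.0660, SE0 = 0.02842, SE1 = 0.02827. Power = Φ(0.364) = 64%.

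| s | Observed Group 2 rate | Observed RR | Power |
|---|---|---|---|
| 1.00 | 16.5% | 0.50 | 81% |
| 0.95 | 15.7% | 0.53 | 73% |
| 0.90 | 14.9% | 0.56 | 64% |
| 0.80 | 13.2% | 0.63 | 44% |
| 0.70 | 11.6% | 0.71 | 24% |

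**Step 4. No true effect.** The true rate is 16.5% in both arms, and Group 2 is observed at 0.165·s. The chance of p < 0.05 is Φ((d − 1.960·SE0)/SE1) + Φ((−d − 1.960·SE0)/SE1).

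For s = 0.80: d = 0.033, SE0 = 0.03162, SE1 = 0.03158. The two terms are 17.95% and 0.13%, together 18%. Almost all of it is in the direction of apparent harm in Group 1.

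At s = 0.90 the chance is 8%, and at s = 0.70 it is 36%. For readmission, assuming 25% in both arms (also from 1.2) and s = 0.80, it is 27%.

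**Step 5. Boundary.** At s = 1 nothing changes: power stays at 81% and the false-positive rate at 5%.

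**The case against.** **Group 2 is not left without assessment.** A reader might infer that nobody asks Group 2 about events. The documents do not support that. Adverse-event evaluation is scheduled for both groups at the diary and at Off Study. Group 2 patients contact the team when the leak stops, and the questioning rule in 7.2 applies at any contact. Section 7.1 requires an adverse event leading to hospitalization to be reported as serious, apart from diagnostic or elective procedures for preexisting conditions. This objection stands, and it confines the gap mainly to events treated at another hospital and unknown to the site. It does not close the gap: the diary offers only a comments box for adverse events, and no mandatory contact carries the Off Study evaluation.

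**The forms may exist elsewhere.** A reader might also infer that no study form asks about the endpoints. That cannot be known, because the case report form (8.3) and the adverse event worksheet (7.3) are not shown. What can be said is that none of the attached diaries and scripts does. Nor should weight be put on the microbiology footnote that seems to belong to no row of the schedule; its marker may have been lost when the table was read from PDF.

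**The illustration favours the concern.** Full capture in Group 1 is assumed, although its script asks about the endpoints only through one open question. No capture rate appears in the documents. This also stands: the figures show sensitivity and do not estimate the bias.

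**Conclusion.** Ascertainment of the 30-day endpoints is not the same by design. Group 1 has up to about 8 to 9 extra occasions for adverse-event questioning, while Group 2 has no scheduled outreach and no mandatory study-end contact. Empyema or admission treated elsewhere is therefore more likely to be recorded in Group 1.

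It would go too far to say that the comparison is shown to be biased, or by how much. The results for 10% and 20% under-capture (risk ratio 0.56 or 0.63, power 64% or 44%, and an 18% chance of a false signal at 20%) depend on the assumed 16.5% control rate, full capture in Group 1 and capture shares that the documents do not give. Under those assumptions the error runs against the intervention, so it would not manufacture a claim of benefit.

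The point should be fixed because unrecorded events cannot be recovered at analysis and the remedy is cheap. It does not by itself invalidate the design.

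**What to change.** 1. In 5.5, make the 14.3 call mandatory at day 30 after discharge for both groups, whether or not the tube is still in place.
2. Add the same fixed questions to the script for both groups: any admission to any hospital, with date; and any diagnosis of, or treatment for, pleural infection or empyema.
3. Request outside records for each positive answer.
4. Add rows for empyema and readmission at day 30, both groups, to the Schedule of Events.
5. State in 3.4, 3.5 and 6.2 that both 30-day endpoints are determined from this common contact plus record review in both arms, and not from the Group 1 calls.

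The cost is protocol and script wording, one short call per patient (up to 560) and some record requests. A single call at the end of the 30-day window leaves the contrast between the randomised strategies as it is.

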6.1 Sample Size Determination

A power analysis was done to determine the sample size. The differences in rates of empyema and 30-day readmission we explored using a two-sided test at an alpha-level of 0.05 and for 80% power. Rate reductions of 25%, 50% and 75% were evaluated. A reduction rate of 50% was selected for empyema and will require 253 patients in each arm for a total enrollment of 506 patients. In allowing an additional 10% for drop outs a total target enrollment of 560 patients will be needed. The 560 patients will give a rate reduction between 25% and 50% for 30-day readmission.

6.2 Statistical Methods

Descriptive Statistics

Descriptive statistics for baseline and clinical variables will be reported as number (percentage) for discrete variables and as mean (SD) or median (range) as appropriate for continuous variables. Baseline demographic and clinical variables will be reported by treatment group. These assessments will help identify potential confounding variables to be used as covariates in multiple variable models when examining the outcomes between treatment arms.

Handling of Missing Data

In the event that we have patients without complete follow-up survival analyses for the outcomes of 30 day empyema and 30 day readmission will be utilized to account for differential patient censoring.

Multiplicity

This study has two treatment arms being compared. No multiple comparison adjustments are planned.

Primary Hypothesis: Assess whether patients receiving antibiotics and twice weekly calls have reduced 30-day **empyema** rates post-discharge compared to patients on standard of care.

The primary analysis will be intention to treat (ITT). The proportion of patients having 30-day empyema in the two treatment arms will be estimated and reported along with a 95% confidence interval. The association of treatment arm with the rate will be assessed using a Chi square test. Additionally, logistic regression will be used to examine the treatment effect accounting for baseline covariates in which there is important imbalance between treatment arms. If not all patients having complete follow-up to 30 days post-discharge then these same analyses will be performed using survival methods, estimates of survival-free of empyema using Kaplan Meier methods and Cox models for the assessment of the association of treatment arm and the risk of empyema. The alpha level will be set at 0.05 for statistical significance.

Secondary Hypothesis 1: Assess whether patients receiving antibiotics and twice weekly calls have reduced 30-day **readmission** rates post-discharge compared to patients on standard of care.

The primary analysis will be intention to treat (ITT). The proportion of patients having a 30-day readmission in the two treatment arms will be estimated and reported along with a 95% confidence interval. The association of treatment arm with the rate will be assessed using a Chi square test. Additionally, logistic regression will be used to examine the treatment effect accounting for baseline covariates in which there is important imbalance between treatment arms. If not all patients having complete follow-up to 30 days post-discharge then these same analyses will be performed using survival methods, estimates of survival-free of readmission using Kaplan Meier methods and Cox models for the assessment of the association of treatment arm and the risk of readmission. The alpha level will be set at 0.05 for statistical significance.

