Reinersman and colleagues evaluated outcomes of patients discharging with an indwelling chest tube from a high volume referral center. At the institution all patients who are discharged with an indwelling chest tube receive standard education from our nursing staff as to dressing changes, changing the dressing when saturated, and noting daily output and changes in output. All patients are instructed on how to check the device for air leak. If they notice the leak has ceased, they are to call for the next available appointment to be seen in clinic for possible chest tube removal. Additionally, all patients receive a standard dismissal education pamphlet summarizing the care of the chest tube and Heimlich valve or mini-Atrium[®]. They found that the rate of empyema was 16.5%, using strict criteria, including all patients with a leukocytosis or fever and an undrained effusion on chest x-ray or CT scan. The rate of readmission with a chest tube in place was found to be 25%.

Reinersman and colleagues found male gender, a history of coronary artery disease and peripheral vascular disease were found to be predictors of empyema (15). Traditional predictors of air leak were analyzed including pleural adhesions, chronic obstructive pulmonary disease, upper, age, use of steroids and decreased body mass index (1-3). These traditional predictors did not contribute to risk of empyema and readmission in their study. The number of patients who were on immunosuppressive medications was too small to determine a difference. The presence of diabetes approached significance but was not a major predictor. Examining reoperative surgery as a surrogate for pleural adhesions also did not show a statistically significant difference in rate of empyema or readmission (p=0.2) (15).

As previously discussed, Brunelli et al. reported that the presence of an air leak greater than 7 days led to a higher rate of empyema compared to patients without air leak or with a shorter duration air leak (14). Reinersman et al. also revealed a temporal relation to number of days with air leak and chest tube related to risk of empyema. The overall number of days with chest tube in place was found to be a predictor of empyema, with an incremental increase per one day with chest tube (HR 1.2, p=0.006). Further, the presence of an air leak and chest tube for more than 14 days markedly increased the risk of empyema (HR 7.6, p=0.047) (15).

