8.3 Case Report Forms

The study case report form (CRF) is the primary data collection instrument for the study. All data requested on the CRF must be recorded. All missing data must be explained. If a space on the CRF is left blank because the procedure was not done or the question was not asked, write "N/D". If the item is not applicable to the individual case, write "N/A". All entries should be printed legibly in black ink. If any entry error has been made, to correct such an error, draw a single straight line through the incorrect entry and enter the correct data above it. All such changes must be initialed and dated. Do not erase or use "white-out" for errors. For clarification of illegible or uncertain entries, print the clarification above the item, then initial and date it. If the reason for the correction is not clear or needs additional explanation, neatly include the details to justify the correction.

Data Management

Data will be entered into a Medidata RAVE database. Medidata RAVE is a secure, customizable Web application designed for collecting study data. Once collected, data can be automatically exported to Microsoft Excel or several common statistical software packages (SPSS, SAS, R and Stata) for analysis. Randomization will take place in the Balance module of Medidata RAVE and will be stratified by enrollment site.

Data Processing

Data will be entered by each research site. Data will be analyzed at the Mayo Clinic Rochester.

Data Security and Confidentiality

Medidata RAVE is a secure database which requires individual log on. Data from each site is only accessible by the site and the data managing site, Mayo Clinic Rochester.

Data Quality Assurance

Medidata RAVE has built in data checks. Source documents may be requested by the data management site, Mayo Clinic Rochester, in order to verify data if needed.

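### Site is a randomization stratum but is absent from the planned tests, and the supportive adjusted model picks covariates by observed imbalance rather than prognostic value

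*Protocol*

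**What the plan says.** **Allocation.** Section 3.1 describes a multicenter randomized trial. The Data Management text in section 8.3 states: "Randomization will take place in the Balance module of Medidata RAVE and will be stratified by enrollment site". No other stratification factor is named.

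**Primary test.** For 30-day empyema, section 6.2 states: "The association of treatment arm with the rate will be assessed using a Chi square test". Readmission has the same test. Site appears in no planned analysis.

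**Adjusted model.** Section 6.2 then adds, as a further analysis, that "logistic regression will be used to examine the treatment effect accounting for baseline covariates in which there is important imbalance between treatment arms". The readmission paragraph repeats the rule ("accounting for baseline covariates in which there is important imbalance between treatment arms"). The candidates come from the by-arm baseline tables: "These assessments will help identify potential confounding variables to be used as covariates in multiple variable models when examining the outcomes between treatment arms". No list is given, and no threshold for what counts as important.

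**Fallback.** If follow-up to 30 days is incomplete, the same analyses are to be done with Kaplan-Meier and Cox methods. The text does not say whether that Cox model carries the imbalance-selected covariates.

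**Known predictors.** Section 1.2 reports from the earlier single-institution series that "male gender, a history of coronary artery disease and peripheral vascular disease were found to be predictors of empyema".

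**The concern.** There are two separate weaknesses.

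First, stratified allocation forces the arms to be balanced within site, so between-site differences in risk cannot contribute to the difference between arms. A pooled chi-square still counts those differences in its variance. If sites differ, the standard error is a little too large: type I error falls below 0.05 and some power is given away.

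Second, in a randomized trial a baseline imbalance is chance. Whether adjustment helps depends on how strongly a covariate predicts the outcome. A rule based on imbalance leaves out a strong predictor that happens to be balanced and admits a weak one that happens not to be. Because the threshold is undefined, the content of the adjusted model is settled only once arm-level data have been seen.

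At stake are a small amount of power in the main comparison and the credibility of the adjusted estimate.

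**Working it through.** **The plan's own figure.** Section 6.1 asks for 253 per arm (50% reduction, 80% power, two-sided 0.05) but does not state the control rate. Assume 16.5%, the empyema rate in section 1.2, falling to 8.25%, so the pooled rate is 0.12375.

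n = [1.96·√(2 × 0.12375 × 0.87625) + 0.8416·√(0.165 × 0.835 + 0.0825 × 0.9175)]² / 0.0825²
= (0.9127 + 0.3889)² / 0.006806 = 249 per arm.

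This is within 3% of 253, so 16.5% is a reasonable working rate.

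**Cost of ignoring site.** Assumed inputs: 5 equal sites, exact 1:1 balance within site, 280 per arm (560/2), control rates p averaging 16.5%, and rates halved at every site under the alternative. The wide spread is 3, 6, 16.5, 25 and 32%. The mild spread is 10, 13, 16.5, 20 and 23%.

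*Type I error of the chi-square.* Its variance uses p̄(1−p̄) = 0.165 × 0.835 = 0.137775. The true within-site variance is the mean of p(1−p).

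- Wide: mean p² = 0.039325, so the within-site term is 0.165 − 0.039325 = 0.125675. The ratio is 0.912 and its root 0.955. Type I error = 2Φ(−1.96/0.955) = 2Φ(−2.052) = 0.040.
- Mild: mean p² = 0.029405, so the within-site term is 0.135595. The ratio is 0.984 and its root 0.992. Type I error = 2Φ(−1.976) = 0.048.
- Equal sites: the ratio is 1 and type I error is 0.05.

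*Power* = Φ[(0.0825 − 1.96·s)/t]. Here t is the true standard error, √{[mean p(1−p) + mean (p/2)(1−p/2)]/280}. For the chi-square, s = √(2 × 0.12375 × 0.87625/280) = 0.02783. For the stratified test, s = √{2 × mean[π(1−π)]/280} with π = 0.75p.

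| Spread | t | s, stratified | Chi-square power | Stratified power | Gain |
|---|---|---|---|---|---|
| Wide | 0.02662 | 0.02694 | Φ(1.050) = 85.3% | Φ(1.116) = 86.8% | 1.5 |
| Mild | 0.02743 | 0.02767 | Φ(1.019) = 84.6% | Φ(1.030) = 84.9% | 0.3 |
| Equal | 0.02761 | 0.02783 | 84.4% | 84.4% | 0 |

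Simulation (40,000 trials) agrees. At 3% to 32%, the chi-square has type I error 0.041 and power 86.1%, against 0.049 and 87.6% for the stratified test. At 10% to 23%, power is 85.2% against 85.6% in one run; repeat runs gave differences of 0.2 to 0.4 points.

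*Sensitivity.* A simulation at 506 patients with 3, 5 or 10 sites gave gains of roughly 0.5 to 1.5 points at a between-site SD of 0.5 on the logit scale, and 2 to 4 points at SD 1.0. The largest, 84.3% against 80.1%, needs 10 sites with control rates from 2.5% to 45.6%.

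**The imbalance rule.** Suppose six independent baseline covariates. The chance that at least one is flagged with no real difference is 1 − 0.95⁶ = 26% at p<0.05 and 1 − 0.80⁶ = 74% at p<0.20. So the undefined threshold largely decides whether the adjusted model adjusts for anything.

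In 3,000 simulated trials per setting (assumed odds ratios 1.3 to 3), selection by imbalance gave power of 80.6% to 82.3%, against 80.8% to 81.8% unadjusted and 81.6% to 84.9% with a fixed list. Type I error under selection was 0.040 to 0.048.

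**Event budget.** With 253 per arm, expected events = 253 × (0.165 + 0.0825) = 62.6, about 63. That supports a short covariate list, but not a string of site indicators as well.

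**The case against.** The strongest reply is that nothing here is invalid. The chi-square errs on the conservative side, the sample size is unaffected, and the loss is visible only if sites differ widely, which the protocol gives no reason to expect. The adjusted model is introduced as an addition to the chi-square, and its selection rule uses baseline data, not outcomes. A covariate list and a threshold are also ordinary SAP content, and the SAP is not shown.

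Most of this stands, and it limits the size of the point. The SAP argument stands only in part: the protocol does not leave covariate choice open but fixes a poor rule for it, and it names the test without the stratum.

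Stronger readings a reader might infer are not supported:

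- *The primary test inflates false positives.* The opposite holds: type I error is at or below 0.05.
- *Choosing covariates by imbalance inflates type I error.* A single fixed rule did not do so in simulation. The problem is discretion and lost precision.
- *Adjustment would bring a large gain.* Section 1.2 gives no effect sizes for sex, coronary artery disease or peripheral vascular disease, so any gain rests on assumed odds ratios.
- *Days with the chest tube should be a covariate because section 1.2 links it to empyema.* The reported predictor is the overall number of days, which accrues after randomization and could be altered by the closer monitoring under test. Adjusting for it could bias the effect.

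**Conclusion.** The point holds as a modest, inexpensive improvement. The analysis does not follow the randomization strata, and the adjusted model is governed by a data-dependent rule with no threshold.

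The cost of ignoring site is nil if sites are alike, about 0.3 power points at assumed rates of 10% to 23%, and about 1.5 points at 3% to 32%, for 5 equal sites and 280 per arm. It reaches 2 to 4 points only under strong heterogeneity. All of this rests on an assumed 16.5% control rate and on assumed site numbers and spreads, none of which the protocol supplies for this purpose.

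The imbalance rule affects the supportive logistic model. It could reach further through the Cox fallback, which is a realistic prospect because section 6.1 allows 10% for dropout, but the text leaves open whether that model is adjusted. The documents do not support calling the primary test invalid or the trial underpowered on this account.

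**What to change.** 1. Make the primary test of 30-day empyema a Cochran-Mantel-Haenszel test stratified by enrollment site, with a stated rule for pooling small sites. Report a site-stratified risk difference with its 95% confidence interval. In the survival fallback, use a site-stratified log-rank test and Cox model.
2. Use the same approach for readmission.
3. Delete the imbalance rule. Name in its place a short list fixed before arm-level data are examined: sex, coronary artery disease and peripheral vascular disease. Handle site by stratification, not by indicator terms, given about 63 expected events. State whether the Cox model uses the same list.
4. Confirm that the case report form records cardiac and vascular history. Section 5.1 and the Schedule of Events name only air leak status and surgical history at baseline, so this may need a small data-collection change as well as new wording.
5. Do not adjust for total days with the chest tube.

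The cost is a little more analysis work, a possible addition to the case report form, and a negligible loss if sites do not differ. Sample size is unchanged.
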